### **Significance and relevance to Veterans and VA patient care mission.**

The proposed study to augment CBCT with intranasal oxytocin and to examine its effects on intimate relationship adjustment, social functioning more generally, and quality of life directly addresses the mission of the VA, as outlined in the VA FY 2018–2024 Strategic Plan. Specifically, the proposed study seeks to advance knowledge of how to help Veterans have good quality of life—which the VA identifies as including satisfying relationships—in three ways: First, findings from the proposed study will inform whether B-CBCT social functioning outcomes can be improved with adjunctive medication. By potentiating the effects of B-CBCT with oxytocin, we could increase the clinical response rate of patients and their loved ones receiving B-CBCT. Second, if oxytocin enhances the mechanisms described in this proposal as predicted, it could further strengthen rationale for providers administering eight-session B-CBCT rather than 15-session CBCT. Effectively truncating CBCT would mean that more patients could be seen by the same number of VA providers, potentially improving Veterans' access to treatment. Greater effectiveness and efficiency of treatment could lead to lower costs to VA. Third, by targeting mechanisms that are salient not only to intimate relationships but all interpersonal relationships (such as trust) oxytocin could help the effects of CBCT extend to other, non-intimate relationships, thereby improving overall quality of life and potentially having downstream effects on other issues facing the VA (such as suicide) which is known to be related to interpersonal difficulties. Lastly, improving Veterans' social environments could help them maintain their gains and respond effectively to future stressors—potentially lowering the likelihood of future need for episodes of care.

## Section 9 - Design and Methods

**9) Describe the research design and the procedures to be used to accomplish the specific aims of the project. Provide a precise description of the planned data collection (include what systems or databases will be used/accessed to gather data), analysis and interpretation. For chart review studies, include the timeframe of collection. Address sample size, inclusion of women and minorities. Define in clear terms exactly what will be done to the human subjects.**

### STUDY DESIGN OVERVIEW:

This pilot study will enroll up to 20 couples (40 individuals) in B-CBCT + OT over this 12-month project. Participants will be recruited from the San Diego VA Healthcare System. Couples will participate in 8 sessions of B-CBCT augmented with 40 IU of intranasal oxytocin administered 30 min before each session. At baseline and post-treatment, dyads will be asked to complete brief assessments of the outcomes described above. After treatment, they will also provide feedback about factors associated with feasibility of methods and treatment engagement. Quantitative and qualitative data will be used to assess the feasibility and acceptability of the intervention and will be utilized in preparing a proposal for an RCT. We will compare within-group effect sizes on PTSD and relationship satisfaction to effects observed within the historical controls from [name] RCT of B-CBCT.

### RESEARCH SITE:

This pilot study will be conducted at the VA San Diego Healthcare System.

### PARTICIPANTS:

Participants will be 20 Veteran couples (i.e., 20 Veterans and their 20 partners; 40 individuals total) who are interested in receiving couples therapy for PTSD and relationship problems. Couples of all genders, ages, and ethnicities will be included. Participants must enroll and participate together as a couple; if one partner is not interested in participating, the couple will not be enrolled, and referrals for alternative individual services will be offered.

**Inclusion criteria** for the study will require one member of the couple be a Veteran enrolled in the San Diego VA Healthcare System with a Posttraumatic Stress Disorder Checklist-5 score of > 33, indicating a likely PTSD diagnosis. Veterans must agree not to receive other individual or conjoint psychotherapy for PTSD during participation in the study. If already on psychoactive medication prior to study referral, Veteran participant must remain on a stable psychoactive medication regimen for at least 45 days.

**Exclusion criteria** will be acute suicidality; psychosis; active substance use disorder; severe ongoing medical problems, including heart disease and neuroendocrinological disorders (e.g., diabetes); uncontrolled hypotension (systolic blood pressure <100 mm Hg) or hypertension (>160/100 mm Hg); pregnancy, delivery in the past 6 months, or current breastfeeding; or severe intimate aggression reported by either partner (established with validated measures). A list of alternative resources will be provided to ineligible participants.

#### DESCRIPTION OF THE BRIEF CBCT INTERVENTION:

CBCT is a manualized couple-based intervention for PTSD designed to simultaneously reduce PTSD and enhance relationship functioning. The brief version of the therapy (B-CBCT) consists of eight 75-minute sessions organized into two phases that build upon each other and includes both in- and out-of-session exercises to increase skill acquisition. Phase 1 (Sessions 1-2) focuses on the rationale for the therapy and establishing safety within the relationship (e.g., recognizing early warning signs of anger, use of conflict management strategies). Phase 2 (Sessions 3-7) focuses on increasing relational satisfaction and undermining PTSD-related distress. The ways avoidance can generalize beyond specific trauma memories and the role of avoidance in maintaining both PTSD and relationship problems are addressed. Couples develop a list of people, places, situations, and feelings that they have avoided as a result of PTSD and begin in vivo exposure exercises to approach these situations in a graduated manner. Special attention is paid to the selection of in vivo approach activities that will address behavioral and experiential avoidance, and concurrently double as shared rewarding activities for the couple. Enhanced dyadic communication is used as an antidote to PTSD-related emotional numbing and avoidance, as well as a means of increasing emotional intimacy. The final session (Session 8) culminates with a discussion of the potential for consolidating newly acquired skills and a review of gains made and challenges expected in the future. B-CBCT will be delivered via video teleconferencing.

#### TREATMENT DELIVERY MODALITY:

Couples must have access to DSL or cable internet service. B-CBCT will be delivered to couples via their personal computer if it is in a private, quiet setting within their home. Project or VA IT staff will be available for home-based equipment set-up if necessary. To assure patient confidentiality and HIPAA compliance, we will use VA-approved CVT software (AK Summit software with FIPS level encryption). The most recent Home-Based Telemental Health Standard Operating Procedures Manual will be used to best implement B-CBCT. Please see Humans Subject document for further participant safeguards in place.

#### DESCRIPTION OF INTRANASAL OXYTOCIN:

A 40 IU dose of oxytocin will be self-administered by the Veteran with PTSD only (not the partner) intranasally 30 minutes prior to the start of each weekly B-CBCT session. A 40 IU dose has demonstrated extensive safety and efficacy, is within the normal dosing range, and is one of the most common concentrations utilized in human research. The medication administration protocol is based on previous research by [name] (Collaborator), a leading oxytocin researcher in the area of PTSD, and others. While intranasal oxytocin has most frequently been used in studies utilizing single doses, several recent published studies of repeated dosing have provided evidence of safety in clinical populations, including a study of once-weekly dosing for eight weeks among Veterans with PTSD conducted by Drs. [name] and [name] (Collaborators).

The study prescriber ([name]) will verify study eligibility and provide prescriptions for oxytocin to the VA Research Pharmacy. Oxytocin will be compounded, refrigerated, and shipped directly to the participant's home with administration and refrigerated storage instructions by Harbor Compounding Pharmacy in Costa Mesa, CA with operational support from the VA Pharmacy, which will be responsible for sending prescriptions and documenting the medication in Veterans' medical charts. Research staff will instruct participants on the correct method of administration to achieve the 40 IU dose and will observe participants' self-administration via Veterans Video Connect (VVC). Participants will blow their nose, exhale through their nose, then spray into one nostril while inhaling, alternating nostrils until the 40 IU dose is achieved. Side effects and adverse events will be evaluated weekly.

## TREATMENT PROVIDERS:

Treatment will be provided by clinicians ("Intervention Specialist" [IS]) who have a Master's degree or higher and a minimum of 2 years of clinical experience. B-CBCT providers, [name], [name], and [name], are trained on B-CBCT and have administered the therapy on a four-year clinical trial to fidelity.

The research pharmacist at VA San Diego ([name]) is facilitating the procurement of intranasal oxytocin from Harbor Compounding Pharmacy in Costa Mesa, CA. [name], a VA psychiatrist, will oversee the prescription of oxytocin.

## ASSESSMENT ADMINISTRATION:

The assessment protocol will include well-validated measurement in the spheres of safety, desirability, and symptoms/functioning for each participant (i.e., Veteran and partner) at baseline, post-intervention (i.e., after all eight sessions have been completed), and three months post-intervention. Depending on participant preference, assessment may be completed over the phone or documents can be returned via encrypted email (using VA Azure RMS). Pre-treatment and post-treatment assessments will occur approximately 20 to 28 weeks apart. The study will also include qualitative interviews with couples to improve study delivery and methods.

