## DATA COLLECTION:

Responses to measures at all assessment time points are collected with each partner individually with the other partner leaving the room to avoid coercion or fear of reprisal if one partner were to disclose disqualifying information such as domestic violence. Participants will complete the following measures prior to study enrollment to determine if inclusion/exclusion criteria are met:

- *PTSD Checklist for DSM-5* (PCL-5; Weathers et al., 2013) – 20-item self-report measure for the past month that assesses symptoms of PTSD based on the DSM-5; scores at or above 33 indicate probable PTSD. Couples will be included if the veteran partner scores at or above 33 on this measure.
- *Columbia-Suicide Severity Rating Scale* (C-SSRS; Posner et al., 2011) – 8-item self-report measure of suicidal ideation, plan, and intent. Individuals who endorse acute suicidality will be excluded from the study.
- *IPV Assessment-Extended* (IPV-5) – assesses behaviors that individuals engage in during conflict with their partner as well as past and current fear and intimidation in the relationship. Couples with individuals who endorse any severe physical assault behaviors in the past year will be excluded from the study.
- *Alcohol Use Disorders Identification Test* (AUDIT; Bohn et al., 1995) – measures problematic substance use. Individuals endorsing symptoms of an active substance use disorder will be excluded.

Additional measures administered at baseline assessment only include:

- *Traumatic Life Events Checklist* (TLEC; Blake et al., 1995) – a 17-item self-report scale that assesses for a lifetime history of exposure to traumatic events (veteran only)
- *Demographic information and past experiences receiving mental health treatment* (both partners)
- *Coronavirus Stressor Survey* – assesses stress related to COVID19 (both partners)

The primary (relationship satisfaction) and secondary (PTSD symptoms, quality of life) outcomes will be assessed with both partners at baseline, post-intervention, and three months post-intervention using the following quantitative measures:

- *Couples Satisfaction Inventory-32* (CSI-32; Funk & Rogge, 2007) – a well-validated measure of relationship satisfaction
- *Changes in Sexual Functioning Questionnaire Male Clinical* (CSFQ-M; Keller et al., 2006) – the male version of a 14-item measure that provides a brief measure of sexual functioning with good construct validity and internal reliability

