Prior to each B-CBCT session, each participant will complete brief self-report assessment measures for the primary and secondary outcomes. The outcomes measures are listed below. The Veteran participant will complete a questionnaire assessing any side effects of the intranasal Oxytocin. If the Veteran participant is able to become pregnant, she will also take a pregnancy test.

- *PCL-5* and *PCL-C* (Weathers et al., 2013) – past-week version for PTSD+ participant and partner respectively
- *Couples Satisfaction Inventory-4 (CSI-4)* (Funk & Rogge, 2007) – a well-validated and brief (i.e., 4 items) measure of relationship satisfaction completed by both partners

No PII will be stored with participants' data; data will be identified by coded study identifier only. Electronic deidentified data will be stored on restricted VA research servers accessible only on VA-networked, password protected computers. Records linking coded study identifiers to participants' identifiable information will be kept separately from any data, and electronic records will be password-protected. Any hard-copy data (e.g., transcribed questionnaires) will be stored in locked file cabinets in locked offices in [name] office space in the San Diego VMRF/HSR&D Building (Building 13), with any identifiable hard-copy data being stored separately from coded research data.

If able to become pregnant (i.e., assigned female at birth, fertile, following menarche and until becoming post-menopausal unless permanently sterile), the Veteran participant will be required to take a pregnancy test (provided by study staff) at baseline assessment and weekly during treatment before self-administration of oxytocin. A participant is considered not able to become pregnant if they are premenarchal, surgically sterile (documented hysterectomy, bilateral salpingectomy, bilateral oophorectomy, and/or tubal ligation), postmenopausal, or assigned male

at birth. These pregnancy tests will be purchased by the study and mailed to Veteran participants who are able to become pregnant only. Veteran participants who are able to become pregnant will be required to verbally confirm a negative result prior to continuing with each oxytocin administration.

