**12.1c) A master list of all VA subjects consented (written or not) under this protocol will be maintained.**

Agree  Disagree

**12.1d) Identify the circumstances under which consent will be obtained including where the process will take place; any waiting period between describing the research and obtaining consent including sufficient time for the prospective participant to consider participation, and any steps taken to minimize the possibility of coercion or undue influence.**

Consent will be obtained from both partners during a Webex or VVC telehealth appointment. Prior to the appointment, the DocuSign document including approved informed consent, HIPAA document, and CA Experimental Subjects Bill of Rights will be sent to the couple. The information in the informed consent document will be discussed with the couple during the telehealth visit. Specifically, both members of the couple will be informed that their participation is voluntary, that all information will be kept confidential [except when information pertaining to threat of harm to self (i.e., suicidal intent) or others (i.e., homicidal intent, child abuse, elder abuse) is disclosed by one or both members of the couple], and that they can terminate participation at any time without negative consequences. They will also be informed that they will complete eight 75-minute therapy appointments and assessment measures three times (baseline, post-

program, and three months post-program). It will be explained that the purpose of this study is to find out whether Brief Cognitive Behavioral Conjoint Therapy augmented with intranasal oxytocin results in improvements in PTSD symptoms and relationship satisfaction. It will also be explained that both members of the couple must participate to be eligible for the study.

If either member of the couple cannot demonstrate sufficient comprehension of the consent information by briefly explaining the purpose and risks and benefits of the study, the couple will not be included in the study and the assessment clinician will refer them for alternative treatment.

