Electronic research data will include audio recordings of B-CBCT sessions as well as responses on self-report assessment surveys. Research data will be collected by hard copy or by phone and will be entered into an electronic data set stored on VA secure local research servers accessible only by authorized users on password-protected computers.

In terms of participant safety monitoring, each participant will be given the telephone number of the PI and study clinician during the consenting process. Participants will be encouraged to call the PI or notify study staff if they experience significant distress from participating in the study. Any study staff will contact the PI about any participant who appears or reports significant distress related to study participation. All such participants will then be contacted personally by the PI and, in cases where the distress is extreme, the PI will decide upon and provide needed services or referrals. The study's exclusion and inclusion criteria provide additional clinical safeguards by identifying appropriate participants for this treatment and excluding high risk patients (i.e., suicidal/homicidal ideation, domestic violence, active SUD, pregnancy /breastfeeding, and hypertension).

This study will include a Data Safety and Monitoring Plan (DSMP) that will be developed in accordance with the National Institutes of Health (NIH) Office of Human Research Protection (OHRP) to assure the appropriate clinical safety monitoring of study subjects participating in this study. Recruitment and safety data are monitored according to the schedule established by the monitoring board, generally every 4-6 months for intervention studies. Quality control and assurance of data entered into the database is discussed above as part of Protections Against Risk. Missing data will be considered as part of the plan for statistical analysis. This study will not include a Data Safety Monitoring Board.

**27.b) Entry of a CPRS Research Informed Consent Note is required when subjects will be admitted as inpatients or treated as an outpatients for research and the study involves research medical care or may affect medical care.**

- *If a Research consent Note is required, then a Research Progress Note should also be entered for each procedure or intervention.*

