Brief Cognitive Behavioral Conjoint Therapy for PTSD With Adjunctive Intranasal Oxytocin (CBCT+OT)

NCT05207436

2/15/23

Data Analytic Plan

Primary analyses with the intent-to-treat sample evaluated change in PTSD symptoms and relationship satisfaction using weekly session, baseline, and post-treatment data analyzed with multilevel linear growth models in the *R* package lme4 and a Kenward-Roger small samples correction. To account for dyadic interdependence, time was nested within individuals and individuals were nested within couples. Analyses included two-intercept models, which produce separate slope and intercept estimates for PTSD+ veterans and non-PTSD+ partners, and a separate interaction model to test for differences between slope and intercept estimates for veterans and partners. PTSD data was composed of veteran PCL-5 and partner/collateral PCL-5 scores. Relationship satisfaction data were CSI-4 scores for both partners; at baseline and post-treatment, the four items comprising the CSI-4 were extracted from the CSI-32 to be included in growth curve analyses.

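### Couples who stop therapy early have no scheduled later outcome, so the intent-to-treat growth model carries them along the fitted line without a check

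*Protocol*

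**What the plan says.** **Timing of outcomes.**
- Protocol Section 9, Assessment Administration, places the two later assessments at "post-intervention (i.e., after all eight sessions have been completed), and three months post-intervention". The three-month visit is counted from the post-treatment one. The same paragraph puts the pre- and post-treatment assessments about 20 to 28 weeks apart.
- Section 9, Data Collection, ties the interim scores to sessions: "Prior to each B-CBCT session, each participant will complete brief self-report assessment measures for the primary and secondary outcomes". These are the PCL-5 (with its partner version) and the CSI-4.
- Three places give the occasions without the completion condition. The Study Design Overview says "At baseline and post-treatment, dyads will be asked to complete brief assessments of the outcomes described above". Data Collection says "outcomes will be assessed with both partners at baseline, post-intervention, and three months post-intervention using the following quantitative measures". Section 12.1d says that couples are told "they will complete eight 75-minute therapy appointments and assessment measures three times".
- Section 6 words the hypotheses as improvement after B-CBCT + OT has been completed.

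**Stopping and missing data.**
- Section 12.1d lets participants stop at any time, and Section 14 foresees withdrawal because of discomfort with the treatment.
- Section 27a says "Missing data will be considered as part of the plan for statistical analysis".
- The SAP says "Primary analyses with the intent-to-treat sample evaluated change in PTSD symptoms and relationship satisfaction using weekly session, baseline, and post-treatment data", fitted with multilevel linear growth models. It has no text on dropout, missing data or sensitivity analysis.

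**The concern.** Both later visits depend on completing therapy, and the interim measures end when sessions end. No section gives an early-termination visit or a rule for following couples who stop. If the Protocol is carried out as worded, such couples enter the growth model through baseline and attended sessions only.

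A likelihood-based growth model handles this by assuming that, given what was observed, the unseen course follows the fitted line. If couples leave because therapy is going badly, and then do worse than the line implies, the satisfaction and PTSD slopes come out too favourable. With no later value and no sensitivity analysis, a reader cannot tell how far the result depends on this. The Study Design Overview says that the within-group effects will be compared with historical B-CBCT results and used in preparing an RCT proposal.

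**Working it through.** **1. What a couple that stops after session k supplies, read literally.** Baseline: yes. Pre-session scores: sessions 1 to k. Post-treatment: not scheduled, because eight sessions were not completed. Three months: not scheduled, because it is counted from post-treatment.

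**2. Figure to reproduce.** There is none. The documents give no dropout rate, power or sample-size derivation, so the rest is an illustration.

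**3. Inputs.**
- From the documents: 20 couples (Section 9); d = 0.38 for the within-group effect of B-CBCT on satisfaction (Section 7); baseline, eight pre-session measures and post-treatment, so 10 occasions; sessions taken "30 minutes prior to the start of each weekly B-CBCT session" as weekly; post-treatment at 20 to 28 weeks.
- Assumed: 20% stopping (4 couples), with 10% and 30% as a range; last session attended spread over 2 to 5 or over 6 to 7.
- Assumed variance settings (intercept SD, slope SD, residual SD): 0.89, 0, 0.45; 0.89, 0.5, 0.45; 0.8, 0.5, 0.6.
- Assumed course of couples who stop: (a) completers' slope; (b) no change throughout; (c) completers' line until they leave, then back at baseline by post-treatment.
- Two time grids, because weekly sessions and a 20 to 28 week interval do not settle how soon after session 8 the assessment falls. Grid 1: sessions at weeks 1 to 8, post-treatment at week 20, 24 or 28. Grid 2: equal steps, post-treatment one step after session 8.

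**4. Direct arithmetic.** Under (b) or (c), the true all-couples change is 0.38 × (1 − 0.20) = 0.304. Under (c), everything observed lies on the completers' line, so the model returns 0.380. The overstatement is 0.380 − 0.304 = 0.076. Under (a), truth and estimate are both 0.380, so the bias is 0.

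**5. Expected model slope.** For one role, with time scaled 0 to 1, the expected generalised least squares estimate is the second element of (Σ Xᵢ′Vᵢ⁻¹Xᵢ)⁻¹ Σ Xᵢ′Vᵢ⁻¹μᵢ, where Vᵢ = ZᵢGZᵢ′ + σ²I and each couple contributes only its observed occasions. The SE is the square root of the matching diagonal element of the inverse. This simplifies the SAP's two-intercept dyadic model: it takes one role at a time with known variances. Results at 20% stopping, (b) and (c) pooled, truth 0.304:

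| Post-treatment value available from | Grid 1 | Grid 2 |
|---|---|---|
| none of the 4 (literal plan) | 0.361–0.380 | 0.329–0.380 |
| 2 of the 4 | 0.330–0.339 | 0.318–0.358 |
| all 4 | 0.299–0.307 | 0.311–0.336 |
| Overstatement, literal plan | 0.057–0.076 | 0.025–0.076 |
| SE, literal plan | 0.13–0.21 | 0.11–0.19 |

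**6. Range of dropout, literal plan.** At 10% the truth is 0.38 × 0.90 = 0.342. The estimates are 0.372–0.380 (grid 1) and 0.355–0.380 (grid 2), an overstatement of 0.013 to 0.038. At 30% the truth is 0.38 × 0.70 = 0.266. The estimates are 0.349–0.380 and 0.300–0.380, an overstatement of 0.034 to 0.114.

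**7. Cross-check.** A separate simulation used equal steps, slope SD 0.4, and couples who stop seen for two or four occasions and then back at baseline. It gave overstatements of about 0.04 to 0.15 over 10% to 40% stopping, and none when they kept their slope.

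**The case against.** The completion wording in Assessment Administration may only explain when post-treatment falls, without making the visit conditional. That paragraph applies to each participant and gives a calendar interval. Three other places list the occasions with no condition, and Section 20 pays by assessment visit, not by session. A reader might infer that the plan excludes couples who stop from follow-up or from the analysis. The documents do not say that. They are silent, practice may have differed, and the model keeps these couples through their observed data. What stands is that the only definition of the post-treatment visit rests on completing eight sessions, and nothing tells staff to assess couples who did not.

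A reader might also infer that the model or the intent-to-treat label is wrong. The documents do not support that either. Missing-at-random is the usual default for a likelihood-based growth model, and leaving it unnamed is only missing detail.

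Section 6 points to change after completion, so the all-couples change of 0.304 is not a target that the documents define. That is fair, but the SAP's intent-to-treat wording points to all enrolled couples, and the two descriptions are not reconciled.

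Finally, the dropout inputs are assumed, the trial is a single-arm pilot, and at 20% stopping the bias is below one SE. All of this stands and keeps the point minor.

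**Conclusion.** The point holds as a small design gap. Read literally, the Protocol schedules no outcome after stopping, and the SAP does not examine what the growth model assumes in its place. With 20% stopping, no net gain in those couples and d = 0.38 in completers, the overstatement is about 0.03 to 0.08 d against an SE of 0.11 to 0.21. It is 0 if couples who stop share the slope. The direction depends on their doing worse than the line, which the documents neither show nor rule out. The effect on the historical comparison cannot be stated, because the documents do not say how that trial followed its own dropouts. A modest improvement is all that is at stake.

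**What to change.** **Protocol, Assessment Administration.** Schedule the post-treatment and three-month assessments for every enrolled couple that has not withdrawn from the study, whether or not it completes eight sessions. Time them from baseline to match when completers are actually assessed. Include the post-treatment value in the primary growth model. This helps but is not complete: in grid 2, values from all four couples still leave 0.311 to 0.336 against 0.304.

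**SAP.** Report how many couples stopped and when. Add one sensitivity analysis that sets the missing post-treatment CSI-4 and PCL-5 of couples who stopped to their baseline value, by multiple imputation with residual noise so that uncertainty is carried. This also covers participants who withdraw from the study, whom the added visit cannot reach. A sentence naming missing-at-random is useful but secondary.

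**If data collection is finished** (the SAP is dated 2/15/23 and written in the past tense), do only the reporting and the sensitivity analysis, and state that couples who stopped contribute data only up to their last session.

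**Cost.** One Protocol sentence and a short SAP paragraph. The assessments are already planned by phone or encrypted email and already have a payment schedule (Section 20). The downside is some staff time to contact couples who stopped, and a possibly smaller estimate.
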